# Visit 1 will be considered as baseline for patient diary card assessments if subject does not have patient diary data prior to Visit 1.

\* Interim visit (< 24 hrs of notification) is required only if subject having clinical failure or PDD or server AE of SAE after OT visit prior to EOT visit. In this case all assessment of interim visit will be mapped to EOT visit as scheduled.

If there is more than one record for a given parameter within a specific visit window, then the non-missing record closest to the target day will be summarized. If there are multiple records on the same day for a parameter, then the average value will be considered for continuous parameters, and the worst value will be considered for the categorical parameters.

Study treatment discontinuation and unscheduled visit will also be considered for deriving the visit window for parameters.

## 6.7. STATISTICAL TESTS

The default significant level will be 5%. All confidence intervals will be computed at 95% and all tests will be two-sided, unless otherwise specified in the description of the analyses.

## 6.8. SAMPLE SIZE ESTIMATION

A total of 310 subjects will be enrolled and dosed. These 310 participants will be enrolled for each indication based on the respective prevalence as mentioned in the table below.

These prevalence values are based on all ARTIs in India.

Study	Indication	Prevalence %
Kumari et al (2016)	AOM	17.6
Acharya et al (2003)	CAP	8.6 (0.5% severe)
Shahid et al (2012)	ABRS	14

The approximate ratio of samples in each indication will be 18:9:14 (AOM: CAP:ABRS). Based on this ratio, at least 136 subjects with AOM, 68 with CAP and 106 with ABRS will be enrolled for the study.

If the proportion of participants reporting at least one TEAE is 37.9% (as observed in Young et al, 2003), and assuming a sample size of 310 participants, it is estimated that the width of the 95% confidence interval would be within +/- 5.43% of the sample proportion (ie, [32.5%, 43.3%]), which equates to the lower and upper bounds of the 95% confidence interval lying within approximately 14% of the estimated proportion.

The sensitivity of the precision is calculated with respect to 5 different proportions estimated as presented below:

Proportion estimate	Sample size	Precision	95% CI
30%	310	5.10%	(24.9%, 35.1%)
35%	310	5.31%	(29.7%, 40.3%)
37.9%	310	5.43%	(32.5%, 43.3%)

40%	310	5.45%	(34.5%, 45.5%)
45%	310	5.54%	(39.5%, 50.5%)
50%	310	5.57%	(44.4%, 55.6%)

## 6.9. SOFTWARE VERSION

All analyses will be conducted using SAS version 9.4 or higher.

## 7. STATISTICAL CONSIDERATIONS

Continuous data will be summarized using the number of subjects (n), arithmetic mean (mean), standard deviation (SD), median, minimum value (min), and maximum value (max) values unless otherwise specified. Categorical variables will be summarized using the frequency counts (n) and percentages (%) for each possible value. Data from unscheduled visits will be included in the by-subject listings.

### 7.1. ADJUSTMENTS FOR COVARIATES AND FACTORS TO BE INCLUDED IN ANALYSES

This section is not applicable for this study.

### 7.2. MULTICENTER STUDIES

This study will be conducted by multiple investigators at multiple centers.

### 7.3. MISSING DATA

Missing data will not be imputed in this study.

### 7.4. MULTIPLE COMPARISONS/ MULTIPLICITY

There is no multiplicity adjustment planned for this study.

Document: \\ieedc-vnasc01\BIOSdata\GSK\BRL25000\PPD  
Author: PPD

\Biostatistics\Documentation\SAP

Version Number: V1.0

Version Date: 18JUL2022

Template No.: CS\_TP\_BS016 Revision 6

Reference: CS\_WI\_BS005

Effective Date: 02Dec2019

## 8. OUTPUT PRESENTATIONS

APPENDIX 1 shows conventions for presentation of data in outputs.

The templates provided with this SAP describe the presentations for this study and therefore the format and content of the summary tables, figures, and listings to be provided by IQVIA Biostatistics.

## 9. DISPOSITION AND WITHDRAWALS

All subjects who provide informed consent will be accounted for in this study.

### 9.1. DISPOSITION

Subject disposition will be summarized based on the ITT population by overall and indication. The following summaries will be included in the disposition table:

- Total number of subjects enrolled in the ITT population
- Number of subjects who completed the study treatment
- Number of subjects who completed the study
- Number and percentage of subjects who discontinued from the study
- Number and percentage of subjects who pre-maturely discontinued the study treatment as well as from the study along with reason for discontinuation.

Percentages will be based on the number of subjects in the ITT population.

A summary of reasons for screen failure and the number of subjects included in ITT population by overall and indication will be presented separately based on the enrolled population. The percentages will be based on the number of subjects in the All Enrolled analysis population.

In addition, summary of visits impacted by COVID-19 pandemic will be generated based on the ITT population by overall and indication.

Subject listings of reasons for study withdrawal, treatment discontinuation and reasons for screen failures for each indication will be provided using ITT and enrolled population respectively.

---

Document: \\ieedc-vnasc01\BIOSdata\GSK\BRL25000\PPD\Biostatistics\Documentation\SAP  
Author: PPD

Version Number: V1.0  
Version Date: 18JUL2022

Template No.: CS\_TP\_BS016 Revision 6

Reference: CS\_WI\_BS005

Effective Date: 02Dec2019

## 9.2. PROTOCOL DEVIATIONS

Protocol deviations are the deviations from the procedure outlined in the protocol. All the important protocol deviations (PDs) will be summarized using ITT population as obtained from Clinical Trial Management System (CTMS) logs. PDs will be identified and discussed with the Investigator/Sponsor in PD review discussion and to finalize analysis set assignment.

Summary of important protocol deviations related to COVID-19 pandemic will also be provided by overall and indication using ITT population.

A subject listing of important protocol deviations identified by the study team will be presented each indication.

## 10. DEMOGRAPHIC AND OTHER BASELINE CHARACTERISTICS

The following demographic data and other baseline characteristics will be presented for the ITT population by overall and indication:

- Derived Age (years)
- Age in categories ( $\leq$  6 months,  $>$  6 months and  $<$  2 years,  $\geq$  2 years and  $<$  5 years,  $\geq$  5 years and  $<$  8 years,  $\geq$  8 years )
- Sex
- Race
- Ethnicity
- Weight (kg)
- Weight in categories ( $\leq$  12kg,  $>$  12 kg and  $\leq$  23 kg,  $>$  23 kg and  $\leq$  40 kg,  $>$  40kg )
- Height (cm)

Baseline characteristics will include vital signs parameters, bowel movements, and radiological assessments (X-Ray of chest and nasal/paranasal sinus), as performed at the time of preliminary visit.

Continuous demographic and baseline characteristics data will be summarized using descriptive statistics. For categorical data, counts and percentage of subjects in each category will be provided.

Subjects listing of demographic characteristics by indication will be provided for ITT population.

Document:	\\ieedc-vnasc01\BIOSdata\GSK\BRL25000	PPD	Biostatistics\Documentation\SAP
Author:	PPD	Version Number:	V1.0

Template No.: CS\_TP\_BS016 Revision 6

Version Date: 18JUL2022

Effective Date: 02Dec2019

Reference: CS\_WI\_BS005

**Baseline Signs and Symptoms:**

The following summaries will be generated for baseline signs and symptoms with counts and percentages -

- Baseline signs and symptoms by indication using ITT population
- Baseline signs and symptoms by severity and indication using ITT population

By-subjects listing of baseline sign and symptoms by indication will be generated.

**Baseline Bowel Habits:**

The following summaries will be generated for baseline bowel habits-

- Descriptive statistics (n, mean, standard deviation, median, minimum, and maximum) on frequency of bowel movements at baseline by indication overall and indication using ITT population
- Summary (counts and percentages) and Descriptive statistics (n, mean, standard deviation, median, minimum, and maximum) on consistency of bowel movements at baseline by indication overall and indication using ITT population

Subject listing of radiographic evaluation by indication will be produced.

## **11. SURGICAL AND MEDICAL HISTORY**

Medical History conditions are defined as those conditions which stop prior to or at preliminary visit. Medical history will be coded using the Medical Dictionary for Regulatory Activities (MedDRA) version 24.1 and will be summarized by system organ class (SOC) and Preferred Term (PT) with counts and percentages based on the intent to treat analysis population. A subject having more than one medical condition/disease within the same SOC/PT will be counted only once for that SOC or PT.

Medical history will be sorted by descending order of system organ class (SOC) and total frequency of preferred term (PT) within each system organ class (SOC).

Past and current medical conditions will also be summarized with counts and percentages using ITT population by overall and indication.

---

Document:	\\ieedc-vnasc01\BIOSdata\GSK\BRL25000\PPD	Biostatistics\Documentation\SAP
Author:	PPD	Version Number: V1.0 Version Date: 18JUL2022

Template No.: CS\_TP\_BS016 Revision 6

Reference: CS\_WI\_BS005

Effective Date: 02Dec2019

## 12. CONCOMITANT MEDICATIONS

Pre-treatment medication is defined as any medication that started and stopped prior to the first dose of study drug.

Concomitant medication is defined as any medication which started before the first dose of study drug AND was ongoing at the time of the first dose of study drug, or started on or after the date of first dose of study drug.

Medications with partially or completely missing start and/or stop dates will be handled as described in Section 6.4.

All medications will be coded using the World Health Organization (WHO) Drug Global dictionary version B3 September 2021.

Concomitant medications will be summarized using anatomical therapeutic class (ATC) level 1 and ingredient by overall and indication for pre-, on and post- treatment based on the ITT analysis population. A subject having more than one medication within the same ATC Level 1 or ingredient will be counted only once for that ATC Level 1 or ingredient. Subjects listings will be provided for concomitant medications.

Concomitant medications will be sorted in descending order of total incidence across Augmentin ES treatment group for the ATC level 1 and in descending order of total incidence for the ingredient within each ATC level 1 class.

## 13. STUDY MEDICATION EXPOSURE

Exposure to study medication in days will be presented for the ITT population.

The total exposure to Augmentin Extra Strength (ES)-600 (amoxicillin/potassium clavulanate 14:1 combination) is calculated based on derivation as mentioned in section 13.1. Subjects who entered treatment period but did not report any treatment dates will be categorized as having zero days of exposure.

Descriptive statistics summary on extent-of-exposure by overall and indication will be presented for study medication exposure using ITT population.

Subject listing of exposure for study medication by indication will also be generated.

Document:	\\ieedc-vnasc01\BIOSdata\GSK\BRL25000\PPD	\\Biostatistics\Documentation\SAP
Author:	PPD	Version Number: V1.0
		Version Date: 18JUL2022
Template No.:	CS_TP_BS016 Revision 6	Reference: CS_WI_BS005

Effective Date: 02Dec2019

### 13.1. DERIVATIONS

Duration of exposure days = (date of last study drug administration – date of first study drug administration) + 1.

## 14. STUDY MEDICATION COMPLIANCE

Subject compliance will be assessed by measuring the number of doses per number of days on drug (refer section 14.1). A minimum of 80% and a maximum of 120% compliance with the study medication regimen will be required for the patient to be considered evaluable per protocol. Subject compliance will be checked through patient diary card and it will be returned to the site at the end of treatment (EOT).

Summary statistics for study medication compliance will be presented by overall and indication using <80%, 80% - 120% and >120% categories with ITT population.

Subject listings of study medication compliance and non-compliance by indication will be presented using ITT population. Each subject will be checked for possible overdosing using the information on maximum recommended dose by body weight provided in APPENDIX 4.

Instances of overdosing, if any, will be listed.

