8.4. Treatment of Overdose

For this study, any dose of Augmentin (ES)-600 greater than 90/6.4 mg/kg/day within a 24-hour time period will be considered an overdose.

Sponsor does not recommend any specific treatment for an overdose.

In the event of an overdose, the Investigator should:

5. Contact the Medical Monitor immediately.
6. Document the quantity of the excess dose as well as the duration of the overdosing in the eCRF.

Further decision regarding dose interruptions or modifications will be made by the Investigator in consultation with the Medical Monitor based on the clinical evaluation of the participant.

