10.3.1. Definition of AE

AE Definition

• An AE is any untoward medical occurrence in a clinical study participant, temporally associated with the use of a study intervention, whether or not considered related to the study intervention.• NOTE: An AE can therefore be any unfavorable and unintended sign (including an abnormal laboratory finding), symptom, or disease (new or exacerbated) temporally associated with the use of a study intervention.

Events Meeting the AE Definition

• Any abnormal laboratory test results (hematology, clinical chemistry, or urinalysis) or other safety assessments (eg, ECG, radiological scans, vital signs measurements), including those that worsen from baseline, considered clinically significant in the medical and scientific judgment of the Investigator (ie, not related to progression of underlying disease).• Exacerbation of a chronic or intermittent pre-existing condition including either an increase in frequency and/or intensity of the condition.• New conditions detected or diagnosed after study intervention administration even though it may have been present before the start of the study.• Signs, symptoms, or the clinical sequelae of a suspected drug-drug interaction.• Signs, symptoms, or the clinical sequelae of a suspected overdose of either study intervention or a concomitant medication. Overdose per se will not be reported as an AE/SAE unless it is an intentional overdose taken with possible suicidal/self-harming intent. Such overdoses should be reported regardless of sequelae.• The signs, symptoms, and/or clinical sequelae resulting from lack of efficacy will be reported as AE or SAE if they fulfill the definition of an AE or SAE. Also, "lack of efficacy" or "failure of expected pharmacological action" constitutes an AE or SAE.

Events NOT Meeting the AE Definition

- Any clinically significant abnormal laboratory findings or other abnormal safety assessments which are associated with the underlying disease, unless judged by the Investigator to be more severe than expected for the participant's condition.
- The disease/disorder being studied or expected progression, signs, or symptoms of the disease/disorder being studied, unless more severe than expected for the participant's condition.
- Medical or surgical procedure (eg, endoscopy, appendectomy): the condition that leads to the procedure is the AE.

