### 14.1. DERIVATIONS

Overall percentage of the study intervention compliance will be calculated as follows:

Compliance = number of doses taken/ (number of days on therapy x 2) x 100%

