## APPENDIX 4. MAXIMUM RECOMMENDED DOSE BY BODY WEIGHT

Body weight (kg) #	Augmentin 600 for oral suspension (ml) twice in day(BID)	Maximum Recommended Dose Administered by the Oral Route (ml) Twice in day(BID)	Body weight (kg) #	Augmentin 600 for oral suspension (ml) twice in day(BID)	Maximum Recommended Administered by the Oral Route (ml) Twice in day(BID)
			21	8.0	10.5
			22	8.4	11.0
3	1.2	1.5	23	8.6	11.5
4	1.6	2.0	24	9.0	12.0
5	2.0	2.5	25	9.4	12.5
6	2.4	3.0	26	9.8	13.0
7	2.6	3.5	27	10.2	13.5
8	3.0	4.0	28	10.6	14.0
9	3.4	4.5	29	11.0	14.5
10	3.8	5.0	30	11.4	15.0
11	4.2	5.5	31	11.6	15.5
12	4.6	6.0	32	12.0	16.0
13	5.0	6.5	33	12.4	16.5
14	5.4	7.0	34	12.8	17.0
15	5.6	7.5	35	13.2	17.5
16	6.0	8.0	36	13.6	18.0
17	6.4	8.5	37	14.0	18.5
18	6.8	9.0	38	14.4	19.0
19	7.2	9.5	39	14.6	19.5
20	7.6	10.0	40	15.0	20.0

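### The SAP's overdose screen uses 120/8.58 mg/kg/day, while the protocol calls anything above 90/6.4 mg/kg/day an overdose

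*SAP*

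**What the plan says.** Protocol 8.4 gives the study's own definition: "any dose of Augmentin (ES)-600 greater than 90/6.4 mg/kg/day within a 24-hour time period will be considered an overdose". The investigator is to contact the Medical Monitor at once and to "Document the quantity of the excess dose as well as the duration of the overdosing in the eCRF".

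SAP section 14 adds a central check: "Each subject will be checked for possible overdosing using the information on maximum recommended dose by body weight provided in APPENDIX 4". It continues: "Instances of overdosing, if any, will be listed".

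Appendix 4 gives two volumes per dose for each weight from 3 to 40 kg. One is the ordinary twice-daily volume. The other is headed as the maximum recommended dose. SAP 14 does not say which column sets the limit, and it neither repeats nor refers to the Protocol 8.4 definition. SAP 3.3 declares no change in analysis from the protocol.

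**The concern.** Both the wording of SAP 14 and the title of Appendix 4 speak of a maximum recommended dose, and only one column carries that heading. A programmer would naturally use it. If it sits above the protocol's limit, the overdose listing omits children whom the protocol classes as overdosed, and the SAP does not declare the departure.

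The other dosing outputs described in the SAP text would not reveal them. Section 13 states: "Exposure to study medication in days will be presented for the ITT population". Section 14.1 defines "Compliance = number of doses taken/ (number of days on therapy x 2) x 100"%, which counts doses and ignores volume. The adverse event listing need not show them either, because Protocol 10.3.1 says: "Overdose per se will not be reported as an AE/SAE unless it is an intentional overdose taken with possible suicidal/self-harming intent". Safety is the primary objective of this trial, so its overdose listing should follow the protocol's definition of overdose.

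**Working it through.** **Inputs**
- Strength, Protocol 6.1 Table 3: 600/42.9 mg per 5 mL, so 600/5 = 120 mg/mL amoxicillin and 42.9/5 = 8.58 mg/mL clavulanate.
- Protocol limit, section 8.4: 90/6.4 mg/kg/day in 24 hours.
- Volumes per dose: SAP Appendix 4, all 38 rows.
- Weight: children of 40 kg or more are excluded (Protocol 5.2). Taking 6 kg as the lightest relevant row is an assumption.

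**Formula:** mg/kg/day = 2 × mL per dose × mg per mL ÷ kg.

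**1. The ordinary column reproduces the planned dose.** At 10 kg, 90 mg/kg/day needs 90 × 10 ÷ (2 × 120) = 3.75 mL per dose. Appendix 4 gives 3.8 mL, or 2 × 3.8 × 120 ÷ 10 = 91.2 mg/kg/day. From 6 to 39 kg the column runs from 89.1 (7 kg) to 96.0 (6 kg). From 7 kg up the highest value is 92.6 (14 kg). So this column is 90 mg/kg/day with rounding.

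**2. The maximum column.** It is 0.5 mL/kg per dose in all 38 rows:
- amoxicillin 2 × 0.5 × 120 = 120 mg/kg/day; 120/90 = 1.333
- clavulanate 2 × 0.5 × 8.58 = 8.58 mg/kg/day; 8.58/6.4 = 1.341

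**3. The gap in daily volume.** Protocol limit = 90 × kg ÷ 120; the other two limits are twice the Appendix 4 volumes.

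| Weight | Protocol limit (mL/day) | Ordinary (mL/day) | SAP maximum (mL/day) | Maximum minus ordinary |
|---|---|---|---|---|
| 6 kg | 4.5 | 4.8 | 6.0 | 1.2 |
| 10 kg | 7.5 | 7.6 | 10.0 | 2.4 |
| 20 kg | 15.0 | 15.2 | 20.0 | 4.8 |
| 39 kg | 29.25 | 29.2 | 39.0 | 9.8 |

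The ratio of maximum to ordinary volume runs from 3.0/2.4 = 1.25 (6 kg) to 3.5/2.6 = 1.346 (7 kg).

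**4. A child who passes.** A 10 kg child given 4.5 mL twice daily receives 4.5 × 2 × 120 ÷ 10 = 108 mg/kg/day amoxicillin and 4.5 × 2 × 8.58 ÷ 10 = 7.72 mg/kg/day clavulanate. The volume is 4.5/3.8 = 1.18 times the ordinary one. Protocol 8.4 calls this an overdose; 4.5 mL is below the 5.0 mL maximum, so the screen does not. With 20 doses in 10 days, compliance is 20 ÷ (10 × 2) × 100 = 100%.

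**5. Why a literal cut at 90 would not work.** Between 6 and 39 kg the ordinary volume itself exceeds 90 mg/kg/day in 25 of 34 rows (28 of 37 if the 3 to 5 kg rows are counted). Correctly dosed children would fill the listing.

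**The case against.** The case on the other side has several parts.

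- **Reading.** SAP 14 echoes the title of Appendix 4, which covers both columns, and it names no cut-off. This stands as a point about wording. But the title still points to a maximum, and only one column is headed so.
- **Tolerance.** The protocol limit equals the planned dose, so some margin is sensible for volumes measured at home. This also stands. It argues for a stated margin tied to the chart volume. It does not justify an undeclared limit one third above the protocol's.
- **Narrow band.** Gross errors are caught: a doubled dose at 10 kg is 7.6 mL against 5.0 mL, and a third daily dose totals 3 × 3.8 = 11.4 mL against 10.0 mL. What passes is over-measurement of up to about 25% to 35%, and neither document gives a clinical consequence for that range. This is correct and limits the weight of the point.
- **Other routes.** Sites must call the Medical Monitor and record the overdose in the eCRF. SAP 9.2 lists important protocol deviations, and signs or sequelae of an overdose are adverse events. The first two routes work only if someone at the site recognises the overdose, and the third only if there is harm. The central screen is most useful when neither happens.
- **Unseen templates.** The listing sentence in SAP 14 may be meant to include eCRF overdoses, and the exposure listing may show volumes. The SAP text does not say so, and the templates are not in the text reviewed.
- **Diary data.** Protocol 6.2 has the diary record the volume to be administered. If that is only the intended volume, no volume screen will find over-measurement at home. This limits any fix.

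**Conclusion.** The concern holds. On the natural reading of SAP 14 the screening limit is 120/8.58 mg/kg/day at every weight, 33% above the protocol's limit for amoxicillin and 34% above for clavulanate. A protocol-defined overdose between the two limits is not flagged. It reaches the listing only if the site recognised it, recorded it in the eCRF, and eCRF overdoses are included.

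The conclusion rests on the maximum column being the one used; the 120/8.58 figure itself is exact. The effect is confined to one descriptive safety listing. The change should be made: the two documents conflict on a safety definition, and the correction is small.

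**What to change.** Change SAP 14 only, so that the listing contains:

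1. every overdose recorded in the eCRF under Protocol 8.4; and
2. every child whose recorded 24-hour volume exceeds twice the ordinary Appendix 4 volume for body weight.

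Show the dose in mg/kg/day and flag separately any above 120 mg/kg/day. This keeps the Appendix 4 maximum as a second tier and screens against the volume the child was meant to receive.

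**Cost.** One or two SAP sentences and one extra listing column, using the diary volume and eCRF record that the protocol already requires. No protocol amendment is needed.

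**Limits.** Some small measuring excesses will be listed; the 120 flag separates them from the larger ones. Rounding in the chart leaves a gap above 90 of at most 92.6 − 90 = 2.6 mg/kg/day from 7 kg up, and 96.0 − 90 = 6.0 at 6 kg, compared with 120 − 90 = 30 now. If the diary holds only the intended volume, item 1 becomes the main source, and the SAP should say so.
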